6.2 Study Population

6.2.1 Approximate Number of Subjects

Approximately 80 Geisinger bariatric surgery patients will participate in this study.

6.2.2 Inclusion Criteria

- Age 18-65 years
- BMI \geq 35 kg/m² at time of surgery

- Primary bariatric surgery completion \leq 18 months
- Understanding of informed consent

6.2.3 Exclusion Criteria

- Pregnancy
- Revision of bariatric surgery
- Significant cognitive impairment that prevents informed consent

6.3 Recruitment

All bariatric surgery candidates that have been cleared by psychology for surgery (~4-6 weeks before surgery), as well as those who completed bariatric surgery but are less than or equal to 18 months post-surgery, will be informed of the study either via mailed letters (see Attached Recruitment Letter), at support groups/classes or at individual pre or postoperative appointments by study staff.

Mailings will be the primary method of recruitment for patients that have completed bariatric surgery within the last 18 months. A list of names, medical record numbers, addresses, phone numbers, and return appointment dates of those who meet the inclusion and exclusion criteria will be pulled by a data analyst. This information will be used for recruitment purposes.

Potentially eligible patients will be called by a member of the study team to discuss the study in more detail, answer any questions, and if interested, a study visit will be scheduled to review the consent form in detail. Patients that agree to participate will then complete the baseline surveys at that time or can take the surveys home to complete and return in a pre-paid envelope. (See Attached Telephone Screening Script/Surveys)

Patients that have not yet completed bariatric surgery will be approached at either a support group/class or at an individual appointment. If they are approached at support group/class, they will be presented the information about the study in a group setting and given a copy of the consent form that can be taken home for consideration. If they are interested in participating, they will be approached to go over the consent form in detail and sign consent at their first post-operative appointment. After the consent is signed and before randomization occurs, the baseline surveys will be completed either in the clinic or they can opt to take the surveys home to complete and return in a pre-paid envelope.

Patients (both pre-op and post-operative) may also be approached at individual appointments. Pre-operative patients would be informed about the study. If they are interested in participating, they will be approached to go over the consent form in detail and sign consent at their first post-op appointment. After the consent is signed and before randomization occurs, the baseline surveys will need completed either in the clinic or they can opt to take the surveys home to complete and return in a pre-paid envelope. Post-operative patients could sign consent that day if interested in participating in the study. Once consent is signed and before randomization occurs, baseline surveys will be completed either in the clinic or they can opt to take the surveys home to complete and return in a pre-paid envelope.

All participants will be randomized following consent and completion of baseline surveys so they will not be aware of which group they are in while completing baseline surveys.

6.4 Study Duration

6.4.1 Approximate Duration of Subject Participation

Subjects will participate in the study for approximately 6-8 months. This includes recruitment and 4 months of group-based treatment or a waiting period for the control group.

6.4.2 Approximate Duration of Study

This study will be completed in approximately one year. The end of the study is the last visit of the last subject or end of collection of data from the patient's electronic health record.

6.5 Procedures

Following enrollment and completion of baseline surveys, participants will be randomized using a computer program developed by the study biostatistician to the BI or UC groups.

Behavioral Intervention: Participants that are randomized to the intervention group will be able to begin treatment sessions at different times points to accommodate new bariatric patients that complete surgery during the study duration. During the course of the study, there will be two 4-month bi-weekly session periods with at least two separate groups per session period. Therefore, there will be at least 4 time points that new patients can begin the process to complete all 8 individualized sessions. We estimate 10-15 patients per bi-weekly group for 60-minute sessions. The intervention will be structured such that each session will function independently (Table 2).

Table 2. Treatment Session Chart

First Round				
Month	Week	Session #	Group #	Milestone
March	Week 1	1	Group 1	First session initiation
	Week 2	1	Group 2	
	Week 3	2	Group 1	
	Week 4	2	Group 2	
April	Week 5	3	Group 1	
	Week 6	3	Group 2	
	Week 7	4	Group 1	
	Week 8	4	Group 2	
May	Week 9	5	Group 1	
	Week 10	5	Group 2	
	Week 11	6	Group 1	
	Week 12	6	Group 2	
June	Week 13	7	Group 1	
	Week 14	7	Group 2	
	Week 15	8	Group 1	
	Week 16	8	Group 2	First session surveys complete
Second Round				
July	Week 1 Session start delay due to July 4 th holiday.			
	Week 2	1	Group 1	Group 1 start
	Week 3	No group meeting		
	Week 4	2	Group 1	
August	Week 5	1	Group 2	Group 2 start
	Week 6	3	Group 1	
	Week 7	2	Group 2	
	Week 8	4	Group 1	
September	Week 9	3	Group 2	
	Week 10	5	Group 1	
	Week 11	4	Group 2	
	Week 12	6	Group 1	
October	Week 13	5	Group 2	
	Week 14	7	Group 1	
	Week 15	6	Group 2	
	Week 16	8	Group 1	Group 1 complete
	Week 17	7	Group 2	
November	Week 18	No group meeting		
	Week 19	8	Group 2	Group 2 complete

*A group three may be added to a session period to accommodate patient schedules if needed.

The intervention will focus on addressing psychosocial changes after surgery, strategies for postoperative diet and adherence, and preventing weight regain (Table 3). Patients will collaboratively set goals for diet, physical activity, adherence and other behavioral changes tailored to the needs of each participant. Session content and intervention duration are evidence-based, derived from a meta-analysis of post-operative interventions aimed at using behavioral management strategies to enhance weight loss following bariatric surgery²⁰.

Confidentiality and group parameters and expectations will be introduced at the beginning of each session where new patients can start (treatment sessions 1&4 of first 4-mo bi-weekly session and treatment session 1 of second 4-mo bi-weekly session). Participants will be provided information regarding prevention of weight regain and resources for tracking and self-monitoring weight, diet and physical activity. Motivation for weight loss and participation in the group will also be discussed.

Sessions will contain a uniform structure to allow for easy transition of members in and out of the group. Sessions will start with an introduction of new members and review of participant progress on their goals and action plan or homework from the previous session. The majority of the session will be spent introducing and discussing new material and participants will be asked to develop a new action plan and state their goals at the end of the session. Make-up sessions will be offered for participants who miss a group.

Table 3. Intervention Content

Session	Primary Content
1	Preventing malnutrition (vitamins, protein intake, etc.)
2	Address problematic eating patterns after surgery (grazing, loss of control over eating, scheduling and emotional eating) Part 1
3	Address problematic eating patterns after surgery (grazing, loss of control over eating, scheduling and emotional eating) Part 2
4	Physical activity for health and wellness (w/side benefit of weight maintenance)
5	Managing special occasions: holidays, family gathering, restaurant eating, and vacations
6	Relationships and social support after bariatric surgery
7	Body Image
8	Taking stock and maintaining progress (relapse prevention)

The full Group Session Interventional Outline is attached.

A member of the research team will remind the participants that randomize to the Intervention Group the day before each session either via phone or email (if participant chooses email communication they will provide the study team with their email address).

Should any participant express significant psychiatric distress in group, such as emotional reactions to weight loss or how relationships are affected, the group leader (a clinical psychology resident) will assess the participant immediately after group and consult with the study PIs ([name] or [name]). The group leader and study PI(s) will refer the participant for further treatment as appropriate. The group leader may also ask disruptive participants to leave group at any time.

Usual Care:

Participants randomized to usual care will complete surveys at postoperative clinic visits or if necessary, via mail. Upon study completion, patients randomized to usual care will be offered the 8 sessions provided to the BI group. This group will run after all study data have been collected.

Table 4. Compensation and Reimbursement

Behavioral Intervention Group	Compensation(Surveys) Reimbursement (Sessions)	Usual Care Group	Compensation (Surveys)
Baseline Surveys	\$50	Baseline Surveys	\$50
Session 1	\$15	N/A	N/A
Session 2	\$15	N/A	N/A
Session 3	\$15	N/A	N/A
Session 4	\$15	N/A	N/A
Session 5	\$15	N/A	N/A
Session 6	\$15	N/A	N/A
Session 7	\$15	N/A	N/A
Session 8	\$50	Final Surveys	\$50
TOTAL	\$205	TOTAL	\$100

Measures:

Surveys for Aims 1-2 will be administered to all participants at post op baseline (within two weeks of signing consent) and then at the completion of the 8 treatment session timeframe for both the BI and UC groups. Aim 3 measures of feasibility and satisfaction will be administered to BI participants only and at one time point, at study conclusion. Demographic, surgical and medical information will be collected from the EMR including weight (kg), height (cm), age at enrollment, sex, race/ethnicity, surgery type, insurance status, diagnoses and medication.

(Surveys are attached).

1. SF-36, Health-Related Quality of Life (HRQoL, primary outcome): As part of the Medical Outcomes Study (MOS), RAND developed the 36-Item Short Form Health Survey (SF-36). The SF-36 is a set of valid, reliable³⁴⁻³⁶, and easily administered QoL measures that have been used in obese populations^{37,38}.
2. PHQ-9, Patient Health Questionnaire (depression): The PHQ-9 is a brief screening tool already integrated into GHS standard of care that screens for depression severity (sensitivity and specificity=88%). Scores of 5=mild depression, 10=moderate, and 15+=severe.
3. State-Trait Anxiety Inventory (STAI, anxiety): The STAI⁴⁰ is a 40-item assessment of anxiety symptoms and scored on a 4-point Likert scale. Internal consistency ranges from 0.86-0.95; test-retest reliability range 0.65-0.75 over a 2-month interval. It has demonstrated good construct and concurrent validity⁴⁰, and has been used in patients with obesity⁴¹.
4. Weight Efficacy Life-Style (WEL)⁴²: The Short form WEL is a 8-item measure that evaluates an individual's sense of self-efficacy in resisting the urge to eat in various situations. Internal consistency ranges from 0.70-0.90 and it has demonstrated sensitivity to change following weight loss interventions with obese populations.
5. The Paffenbarger Physical Activity Questionnaire (PPAQ)⁴³: The PPAQ is an 8-item, self-administered questionnaire designed to measure participation in leisure time. Respondents report the number of city blocks they walk and flights of stairs they climb on a typical day, as well as to list the frequency and duration of any sports or recreational activities they participated in over the past year. From these questions, a physical activity index (PAI) is computed, providing an estimate of energy expenditure. The PPAQ is used in bariatric surgery research⁴⁴.
6. Loss of Control Over Eating Scale-brief⁴⁵: The 7-item version of the LOCES is a brief measure of the experience of loss of control over eating over the past 28 days and is

[figure not shown]
scored on a 5-point Likert scale. The brief version of the full 24-item measure has demonstrated high internal consistency (0.93) and test-retest reliability ($r=0.82$) among non-clinical populations. The 7-item version is highly correlated with the 24-item version of the measure ($r=0.96$), which has also demonstrated good convergent and discriminant validity and was subjected to a more rigorous development and validation process than alternative measures.

7. Emotional Eating Scale (EES)⁴⁶. The EES is a 25-item scale that evaluates an individual's urge to eat while experiencing a range of emotions. The measure has demonstrated good discriminate validity, test-retest reliability, and sensitivity to change following treatment for weight loss and/or binge eating.
8. Social Adjustment Scale (SAS-SR)^{47,48}: The Short form SAS-SR is a 24-item measure of functioning in 6 social domains and covers four categories: 1) performance at expected tasks; 2) amount of friction with people; 3) finer aspects of interpersonal relations; and 4) feelings and satisfactions. Questions are on a 5-point scale, with higher scores indicating more impairment. The SAS-SR generates 7 mean scores plus an overall mean. Internal consistency for the overall score was moderate ($\alpha=0.74$)⁴⁷. Validity evidence includes appropriate patterns of mean differences, significant correlations with clinical ratings, and sensitivity to change^{48,49}.
9. Adherence: Compliance with postoperative bariatric surgery clinic appointments, including missed visits/no shows, will be obtained from the EMR. Dietary adherence will be measured by 9-point Likert scale ("How well are you following the diet plan given to you by the dietitian?") developed for use in bariatric surgery research⁵⁰.
10. Patient satisfaction: Satisfaction will be measured using bariatric surgery postoperative satisfaction instruments^{10,51}.

6.5.1 Study Time and Events Table

Study Month	1	2	3	4	5	6	7	8	9	10	11	12
IRB Completion												
Recruitment BI + UC, Baseline Measures (n=80)												
Intervention, BI group (n=20), group 1												
Intervention, BI group (n=20), group 2												
Data Analysis												
Manuscript and Grant Preparation												

Figure 6.5.2: Study Flow Diagram

6.6 Primary Endpoints

The primary endpoint will be quality of life. Obesity is associated with diminished quality of life (QoL) and QoL is frequently cited as a primary reason that patients pursue bariatric surgery. Evaluating QoL emphasizes patient experience and perception and provides a measurement of treatment efficacy beyond weight loss. In this application, we propose to evaluate the effect of an innovative postoperative support program targeting quality of life, psychosocial functioning and adherence to behavior change in Geisinger Health System (GHS) bariatric surgery patients.

6.7 Secondary Endpoints

Secondary endpoints include differences in psychosocial functioning (mood, eating behaviors) and adherence (diet, physical activity, appointments), as well as patient satisfaction, treatment feasibility and attrition.

6.8 Statistics

[name], the Obesity Institute biostatistician, will perform the statistical analyses for this study.

6.8.1 Statistical Analysis Plan

Randomization will be conducted using randomization schema generated by the Biostatistician. Randomization to UC or BI will occur following consent. It is plausible that yellow light patients may experience greater benefit from the intervention. We will examine the comparability of demographics characteristics between two groups at baseline. If baseline demographic factors are not balanced between the two groups, we will then adjust for these factors during final analyses.

The primary outcomes will be the difference in mean HRQoL scores (emotional scale) as assessed by the SF-36 between the BI and UC groups at postoperative month 4 (assessment time frame will be postoperative month 1 to month 4). Continuous variables will be analyzed using independent t-tests. We will evaluate the appropriate assumptions using Shapiro–Wilk or Kolmogorov–Smirnov tests (normality) and a Brown–Forsythe test or a Q–Q plot (homogeneity of variance). Should the normality assumption be violated, we will then attempt transformations. If necessary, ANCOVA will be used to control for wave (1 vs 2) or other baseline covariates.

Secondary outcomes include differences between groups in the remaining HRQoL scales. Similar methods as described for the primary outcome will be used for the secondary outcomes. Additionally, within group analyses (secondary) will use paired t-tests. Categorical variables will be analyzed by chi-squared tests.

We will conduct intent-to-treat analysis to determine differences in primary and secondary outcomes using data from all randomized participants. Missing data will be handled using multiple imputation⁵⁵. We will also conduct sensitivity analyses such as best and worst case analyses⁵⁶.

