2 ABSTRACT

Rationale: Bariatric surgery patients may experience significant psychosocial changes after surgery, but little psychological support is available beyond support groups postoperatively. Psychosocial changes after surgery, including mood fluctuations, interpersonal issues and substance use, have the potential to lower quality of life and interfere with adherence to the postoperative diet and lifestyle, diminishing weight loss outcomes.

Objective: We will evaluate the effect of a postoperative support program targeting quality of life, psychosocial functioning and adherence to behavior change in Geisinger Health System (GHS) bariatric surgery patients.

Design and Methods: This prospective, randomized pilot trial will evaluate a comprehensive postoperative behavioral support intervention using a 4-month bi-weekly program (BI group) in 40 bariatric surgery patients (all procedure types) from the GHS Center for Nutrition and Weight Management (CNWM), compared to 40 usual care (UC) patients that completed bariatric surgery within one year. The primary outcome will be the difference in quality of life (as measured by the Short Form-36) between groups, as well as differences in psychosocial functioning (mood, eating behaviors) and adherence (diet, physical activity, appointments). Secondary outcomes will include patient satisfaction, treatment feasibility and attrition. Outcomes will be assessed at baseline and treatment completion (4 months). The intervention (BI group) will focus on addressing psychosocial changes after surgery, strategies for postoperative diet and adherence, and preventing weight regain. Patients will collaboratively set goals for diet, physical activity, adherence and other behavioral changes tailored to the needs of each participant. Intervention patients will attend 8, one-hour bi-weekly treatment sessions in a 4-month time period.

Significance: Knowledge gained will help to fill the gaps in understanding regarding the psychosocial benefits of enhanced behavioral support following bariatric surgery, as well as to improve the quality of patient care at GHS and address the obesity epidemic by providing patients the best possible opportunity for long-term weight loss success.

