6 STUDY DESIGN

6.1 Description

This prospective, randomized pilot trial will evaluate a comprehensive postoperative behavioral support intervention using a 4-month bi-weekly program (BI group) in 40 bariatric surgery patients (all surgical procedure types) from the GHS Center for Nutrition and Weight Management (CNWM) compared to 40 usual care (UC) patients. Participants will be randomized to BI or UC using a computer program. Treatment will occur in two session periods to accommodate patients who complete surgery during the study duration.

We will recruit preoperative bariatric surgery patients who are close to their surgery date as well as those who completed bariatric surgery within 18 months. Participants will not be consented until surgery completion. Patients will be recruited via U.S. mail, as well as at support groups/classes and clinic appointments. We anticipate that of the ~25 surgeries conducted monthly, recruitment will take approximately 6 months to recruit 80 patients on a rolling basis. We will run two, possibly three, biweekly groups simultaneously if needed to accommodate patients available for day or evening groups. The primary outcome will be the difference in quality of life postoperatively, between groups, as well as differences in psychosocial functioning (mood, eating behaviors) and adherence (diet, physical activity, appointments). Outcomes will be assessed at time of enrollment and then at after completion of 8 treatment sessions (BI group). Final outcomes assessments will be distributed to BI and UC patients at the same time to maintain consistent data collection intervals between the groups. Secondary outcomes will include patient satisfaction.

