6.8.2 Statistical Power and Sample Size Considerations

Previous research⁵⁴ indicates that bariatric surgery patients report mean (SD) SF-36 subscale scores before and after surgery of:

	Preoperative	Postoperative	Effect Size
Role - Emotional	74.9 (34.4)	92.3 (22.1)	0.56 SD
Mental Health	70.5 (17.4)	74.6 (18.9)	0.2 SD
Mental Health Composite Score	48.9 (10.1)	52.1 (8.4)	0.3 SD

We aim for a difference of 2/3 standard deviation in scores between groups at 4 months postoperatively. A sample size of 40 participants per group will have 83% power to detect an effect size of 2/3 SD using a two group t-test with a 0.05 two-sided significance level. If the effect size is small than 2/3 SD, we will still be able to assess the level of confidence on the observed differences that will be used to design a large study. When the sample size in each group is 40, a two-sided 95.0% confidence interval for the difference of two means in mental health composite score will extend 4.4 from the observed difference in means, assuming that the common standard deviation is known to be 10.1 and the confidence interval is based on the large sample z statistic.

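### The primary SF-36 comparison is set at postoperative month 4, but the only follow-up survey is timed by the 8-session program, in patients up to 18 months after surgery

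*Combined protocol and SAP*

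**What the plan says.** Section 6.8.1 defines the primary outcome as the difference in mean SF-36 scores (emotional scale) "between the BI and UC groups at postoperative month 4 (assessment time frame will be postoperative month 1 to month 4"). Section 6.8.2 sizes the trial on the same clock: "We aim for a difference of 2/3 standard deviation in scores between groups at 4 months postoperatively".

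The data-collection sections use a different clock. The abstract (section 2) says "Outcomes will be assessed at baseline and treatment completion (4 months"). Section 6.1 says "Outcomes will be assessed at time of enrollment and then at after completion of 8 treatment sessions (BI group") and adds "Final outcomes assessments will be distributed to BI and UC patients at the same time to maintain consistent data collection intervals between the groups". The Measures part of section 6.5 agrees: a baseline survey within two weeks of consent, then one survey at the end of the 8-session period in both arms.

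On who enters, section 6.1 recruits patients close to their surgery date "as well as those who completed bariatric surgery within 18 months". Sections 6.2.2 and 6.3 repeat the 18-month limit. The abstract instead describes usual-care patients as within one year of surgery.

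Section 6.8.1 also requires an intent-to-treat analysis "using data from all randomized participants", with multiple imputation for missing data. On adjustment it says "If necessary, ANCOVA will be used to control for wave (1 vs 2) or other baseline covariates". Time since surgery is not named.

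**The concern.** The analysis sections count from the operation. The survey schedule counts from consent and from the program. The two coincide only for patients who start the program soon after surgery, and eligibility extends far beyond that.

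Read literally, a patient enrolled after postoperative month 4 can never have a value at the primary time point, and even the baseline falls outside the stated window. Yet the plan wants every randomized patient in the analysis and missing values imputed. An analyst following section 6.8.1 to the letter would have to treat the primary outcome as missing by design for these patients, or quietly substitute the end-of-program survey.

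Reporting is also at stake. Sections 4 and 6.8.2 say the data will support grant applications and the design of a larger study. An effect described as arising four months after surgery would misdescribe a survey taken, for some patients, well over a year after it.

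**Working it through.** **1. The plan's own figures.** Inputs from section 6.8.2: 40 per group, effect 2/3 SD, two-sided 0.05, two-group t-test.
- Noncentrality = (2/3) × √(40/2) = 2.981, with 78 df and critical t = 1.991. Power = 83.8%, against 83% stated.
- Confidence interval half-width = 1.96 × 10.1 × √(2/40) = 4.43, against 4.4 stated.

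Both reproduce. Neither formula contains a time point, so re-anchoring the endpoint changes neither.

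**2. The two clocks side by side.**

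| Item | Counted from | Where |
|---|---|---|
| Primary comparison, month 4 (window months 1 to 4) | surgery | 6.8.1 |
| Target difference of 2/3 SD at 4 months | surgery | 6.8.2 |
| Baseline survey | consent | 6.5 Measures, 6.1 |
| Only follow-up survey | program (8 sessions), both arms together | 2, 6.1, 6.5 Measures |
| Entry, up to 18 months | surgery | 6.1, 6.2.2, 6.3 |

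No row schedules a survey by surgery date.

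**3. When follow-up falls after surgery.** In Table 2, session 1 to session 8 runs over weeks 1–15 and 2–16 (round 1) and weeks 2–16 and 5–19 (round 2). Each is 14 weeks. With 365.25/12/7 = 4.348 weeks per month, 14/4.348 = 3.22 months.

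Months since surgery at session 8 = months since surgery at session 1 + 3.22:
- start at month 6: 9.2
- start at month 12: 15.2
- start at month 18: 21.2

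Any wait between enrolment and the first group adds to these. With the nominal 4-month program length, the last figure is 22.

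**4. Entry at session 4.** Section 6.5 also lets patients join round 1 at session 4. In Table 2 that is week 7 (Group 1) or week 8 (Group 2), leaving 8 weeks and five sessions (4 to 8) to the end of the round. Section 6.5 nevertheless expects all eight sessions to be completed. The documents do not say whether these patients are surveyed after their eighth session or at the end of round 1, when Table 2 marks the surveys as complete. On the second reading follow-up comes 8/4.348 = 1.84 months after entry. The figures in step 3 therefore assume that the survey follows all eight sessions.

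**5. Cost of an optional covariate for months since surgery.** With no prognostic value, 77 df alone gives 83.7% power. Allowing also for average chance imbalance (variance inflated by 1/(1 − 1/79)) gives 83.3%. The loss from 83.8% is at most about 0.5 percentage point.

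**The case against.** The strongest reply is that this is one misplaced word. The abstract ties 4 months to treatment completion, round 1 of Table 2 runs over four calendar months, and every data-collection section agrees on when the survey occurs. There is one follow-up dataset, so nobody must choose between rivals. On this view the authors meant month 4 of the program and only the label is wrong.

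Much of this stands. The program reading is the sensible one, and no second dataset exists. But the analysis plan does not say so. It uses the postoperative clock in both 6.8.1 and 6.8.2, and no other section corrects it. The time point of a primary endpoint should not have to be inferred.

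The reply is also right to limit what follows. A reader might infer any of these, and the documents support none of them:
- **The arm comparison is biased.** Patients are randomized and both arms are surveyed together, so the mismatch alone creates no difference between arms.
- **The power is wrong.** It has no time input, and the 2/3 SD target is standardized. Section 6.8.2 gives no post-surgery time for its reference scores, so nothing shows that the target depends on month 4.
- **Almost no patient fits, including the newly operated.** The documents give no distribution of time since surgery and no date for the first postoperative visit, where the newly operated consent. The protocol also uses months nominally, so a difference of a week or so between the window and the program carries no weight.

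**Conclusion.** The concern holds as an internal contradiction in the definition of the primary endpoint, and it should be fixed. Sections 6.8.1 and 6.8.2 name a time after surgery at which no survey is scheduled, and for patients enrolled after postoperative month 4 that time has gone before baseline. The 21.2-month figure assumes a first session at month 18, the 14-week span in Table 2, and a survey after all eight sessions. The number of patients affected cannot be stated from the documents. The consequence is confined to what the primary result means and how it can be reported. The treatment comparison remains valid and the sample size stands.

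**What to change.** **Required.** In 6.8.1 and 6.8.2, replace the postoperative-month wording with: the final survey at completion of the participant's 8-session timeframe, given at the same calendar time to BI and UC participants of the same entry cohort, regardless of sessions attended. Do not add that this is 4 months after the first session unless that is reconciled with the 14 weeks in Table 2. State whether the survey for session-4 entrants in round 1 follows their eighth offered session or the end of the round, and apply the same rule to both arms. Report the range of time since surgery at follow-up.

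**Optional.** Prespecify months since surgery at baseline as a covariate in the primary model. ANCOVA is already allowed, but only if judged necessary, and section 8.2 already lists the date of surgery among the extracted data.

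**Separately.** Reconcile the abstract's one-year wording with the 18-month criterion.

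**Cost.** Wording in two subsections and the abstract, plus one small operational rule: each participant, including those in usual care, is given an entry cohort at randomization so that the shared survey date is defined. The covariate, if adopted, costs one degree of freedom and at most about 0.5 percentage point of power. No extra patients, visits or procedures are needed.

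### The primary month-4 SF-36 comparison is not fixed to one model in advance, and the pre-randomisation SF-36 score is not named as a covariate

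*Combined protocol and SAP*

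**What the plan says.** Section 6.8.1 defines the primary outcome as the between-arm difference in mean SF-36 score (emotional scale) at month 4, and gives the default test: "Continuous variables will be analyzed using independent t-tests".

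Two sentences in the same section can change that model:
- "If baseline demographic factors are not balanced between the two groups, we will then adjust for these factors during final analyses"
- "If necessary, ANCOVA will be used to control for wave (1 vs 2) or other baseline covariates"

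Neither sets a threshold or a test, and neither gives a closed list of covariates. The baseline SF-36 score is not named, although the second sentence would permit it. A third sentence, "Should the normality assumption be violated, we will then attempt transformations", opens another branch: normality tests are named, but no cut-off and no transformation.

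The baseline score will be available. Section 6.5 (Measures) says "Surveys for Aims 1-2 will be administered to all participants at post op baseline (within two weeks of signing consent", and section 6.3 says "All participants will be randomized following consent and completion of baseline surveys".

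Section 6.8.2 bases power on an "effect size of 2/3 SD using a two group t-test with a 0.05 two-sided significance level", giving 83% with 40 per arm. It adds that the confidence attached to the observed difference will help design a larger study, and quotes a half-width of 4.4 points for the mental composite.

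**The concern.** A pre-randomisation measurement of the outcome itself is often the most useful covariate a trial has. Here it is collected from everyone, yet the default analysis ignores it. The balance rule covers demographics only, so a chance difference in the baseline SF-36 score would not set it off.

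The open conditions also leave the primary result undetermined. Two analysts following section 6.8.1 on the same data could reasonably fit different models and report different estimates, intervals and p-values, and nothing says which is primary.

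Both matter more in a pilot whose interval is to feed the next trial's design. A wider interval than necessary costs information, and an interval from an unsettled model is harder to use.

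**Working it through.** **Inputs.** From section 6.8.2: 40 per arm, two-sided 0.05, effect 2/3 SD; composite SD 10.1 and half-width 4.4; Role-Emotional postoperative mean 92.3, SD 22.1. The documents do not give the correlation r between baseline and month-4 scores, so r = 0.2, 0.3, 0.5 and 0.7 are assumed. All figures take 80 complete cases.

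**1. The plan's own figures.** The t-test noncentrality is (2/3) × √(40/2) = 2.98 on 78 df. Power is 83.8%, in line with the stated 83%. The half-width is 1.96 × 10.1 × √(2/40) = 4.43, in line with 4.4.

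**2. ANCOVA on the baseline score, roughly normal outcome.** The residual SD is multiplied by √(1 − r²), with 77 df. To allow for chance baseline imbalance, the noncentrality is d/√(1 − r²) × √20 × √(1 − R²), averaged over R² ~ Beta(1/2, 39). The half-width is 4.43 × √(1 − r²) × 1.0065, where 1.0065 is the mean inflation from imbalance.

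| Analysis | Power at 2/3 SD | Power at 0.5 SD | Composite half-width |
|---|---|---|---|
| t-test | 83.8% | 59.8% | 4.43 |
| ANCOVA, r = 0 | 83.3% | 59.3% | 4.46 |
| ANCOVA, r = 0.2 | 84.7% | 61.0% | 4.37 |
| ANCOVA, r = 0.3 | 86.6% | 63.3% | 4.25 |
| ANCOVA, r = 0.5 | 92.2% | 71.7% | 3.86 |
| ANCOVA, r = 0.7 | 98.4% | 86.7% | 3.18 |

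The break-even correlation at 2/3 SD is about 0.12.

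**3. Exposure to chance imbalance.** The baseline difference between arms has standard error √(2/40) = 0.22 SD, so its 95% range is ±0.44 SD. An imbalance at that limit moves the unadjusted month-4 difference by r × 0.44, that is 0.13, 0.22 or 0.31 SD at r = 0.3, 0.5 or 0.7.

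**4. If the emotional scale is Role-Emotional.** Step 2 does not carry over. Two-thirds of 22.1 is 14.7, and 92.3 + 14.7 = 107.0, above the scale maximum of 100. A 2/3 SD difference can be placed only below 92.3, for example usual care at 92.3 − 14.7 = 77.6 and intervention at 92.3. This was simulated with a latent normal score cut to four levels (0, 33.3, 66.7, 100; assumed), fitted to mean 92.3 and SD 22.1, with both arms at 92.3 at baseline and the usual-care latent mean lowered at month 4. The usual-care SD then becomes about 35.5. Power is about 60% for the t-test, and about 60 to 61%, 63% and 71% for ANCOVA at latent r = 0.3, 0.5 and 0.7.

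**5. How often the balance rule might fire.** This depends on a criterion that the plan does not give. If unbalanced meant p < 0.05 on any of four independent demographics (say age, sex, race/ethnicity and insurance, all listed in section 6.5), the chance is 1 − 0.95⁴ = 18.5%. This is illustrative only; another criterion would give another figure.

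**The case against.** The strongest reply is that nothing here is wrong as it stands. A t-test is valid in a randomised trial, the sample size arithmetic is right, and the plan already allows ANCOVA for baseline covariates. The gain rests on a correlation that the documents do not supply, and at 0.3 or less it is at most 2.8 points of power (86.6 − 83.8). All of that stands. It limits the size of the point, but permission to adjust is not a decision to adjust, and the primary model remains open.

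Three stronger readings are tempting.
- **Inflated type I error.** Always reporting the smaller of the t-test and ANCOVA p-values would raise it to roughly 6.5% to 8% at r = 0.3 to 0.7. That is a worst case. The documents describe no such selection, and either model fixed in advance holds about 5%.
- **Conflicting conclusions.** At 2/3 SD the two models disagree on significance in about 4/6/11/15% of simulated trials at r = 0.2/0.3/0.5/0.7. This mainly restates the power gain: at r = 0.5, 9.8 of the 11.0 points are trials where only ANCOVA is significant. It also uses a covariate that the plan does not name.
- **Demographic adjustment changes the answer.** The figure in step 5 says how often the rule might fire, not that the estimate would move. Adjusting for a demographic weakly related to SF-36 changes little.

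**Conclusion.** The point holds as a matter of precision and prespecification; the planned test and its power are not in error. Section 6.8.1 does not fix one primary model and leaves the most natural covariate unnamed. That gap is certain from the text.

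The size of the benefit is not. For a roughly normal score such as the mental composite, it runs from negligible (r of 0.3 or less) to substantial (about 8 points of power at r = 0.5, and a half-width of 3.86 instead of 4.43). For Role-Emotional it is near nil at latent r = 0.3 and moderate above. These figures assume r and 80 complete cases, although the plan itself expects missing data. The change should be made because it settles the primary analysis at almost no cost, even if r proves low.

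**What to change.** In section 6.8.1, prespecify one primary model: ANCOVA of the month-4 score on arm and the baseline value of the same SF-36 score, fitted whatever the observed balance. This requires the emotional scale to be tied to one named SF-36 score. Replace the balance-triggered rule and the conditional ANCOVA sentence with this model, and keep the unadjusted t-test as a supportive analysis. Use the same model for continuous secondary outcomes that have a baseline measure, and include the baseline score in the multiple imputation model.

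Wave should not enter by default. Section 6.5 describes session periods through the intervention sessions ("Participants that are randomized to the intervention group will be able to begin treatment sessions at different times points"), so wave would first need a definition that applies to both arms and is fixed before randomisation.

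The cost is SAP wording; no new data are needed. If the baseline score turned out to be uninformative, power at 2/3 SD would fall by about 0.5 percentage point, from 83.8% to 83.3%.
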